10.2. Adverse Events

Adverse events (AEs) will be coded using the Medical Dictionary for Regulatory Activities (MedDRA) Version 21.1. Summaries of AEs will include only treatment emergent AEs (TEAEs) defined as AEs with an onset date/time on or after the date/time of first treatment. AEs with completely missing onset dates/time will be considered as TEAEs. If AE onset date/time is partially missing, the AE will be considered as TEAE unless the non-missing part of date/time proves it started prior to the first treatment date/time.

AEs will be summarized using the number and percent of subjects reporting each system organ class (SOC) and preferred term (PT) and sorted alphabetically by SOC and by descending frequency of PT within SOC. Subjects who experienced multiple events within the same SOC will be counted once in the SOC summary. Subjects who experienced multiple occurrences of events with the same PT will be counted once in the PT summary. Percentages will be calculated using the total number of subjects in the Safety population.

The following summary tables for AEs will be presented:

- Overall Summary of Treatment Emergent Adverse Events (TEAEs), All Causalities
- Overall Summary of Treatment Emergent Adverse Events (TEAEs), Study Drug Related
- Treatment-Emergent Adverse Events (TEAEs) by System Organ Class and Preferred Term, All Causalities
- Treatment Emergent Adverse Events (TEAEs) by System Organ Class and Preferred Term,
 Study Drug Related
- Serious Treatment-Emergent Adverse Events (TEAEs) by System Organ Class and Preferred Term, All Causalities
- Serious Treatment Emergent Adverse Events (TEAEs) by System Organ Class and Preferred Term, Study Drug Related

- Treatment-Emergent Adverse Events (TEAEs) by System Organ Class, Preferred Term, and Maximum Severity, All Causalities
- Severe Treatment Emergent Adverse Events (TEAEs) by System Organ Class and Preferred Term, All Causalities
- Severe Treatment Emergent Adverse Events (TEAEs) by System Organ Class and Preferred Term, Study Drug Related
- Treatment-Emergent Adverse Events (TEAEs) Leading to Permanent Discontinuation of Study Drug by System Organ Class and Preferred Term, All Causalities
- Treatment Emergent Adverse Events (TEAEs) Leading to Permanent Discontinuation of Study Drug by System Organ Class and Preferred Term, Study Drug Related
- Treatment-Emergent Adverse Events (TEAEs) of Special Interest by System Organ Class and Preferred Term, All Causalities
- Treatment-Emergent Adverse Events (TEAEs) Occurred in > 1 Subject by System Organ Class and Preferred Term, All Causalities
- Treatment Emergent Adverse Events (TEAEs) Occurred in > 1 Subject by Preferred Term, All Causalities

For the summary of TEAE by maximum severity, if a subject experiences more than 1 occurrence of the same AE, the occurrence with the greatest severity will be used in summary tables.

TEAEs related to study drug/study procedure are those that are identified as reasonable possibility. If relatedness is missing, the AE will be considered TEAE related to study drug/study procedure. In addition TEAEs that occurred in > 1 subject at the PT level will be summarized by SOC and PT, and also by PT.

Subject listings will be presented for all TEAEs, TEAEs of special interest, serious TEAEs, TEAE leading to permanent discontinuation of study drug, Death and Pre-treatment AEs.

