## Documentation and Reporting of Adverse Events

Adverse events should be reported and documented in accordance with the procedures outlined below. All AEs occurring during the study must be documented on the relevant CRF pages. The following data should be documented for each AE:

- · Description of the symptom event
- · Classification of 'serious' or 'not serious'
- Severity
- Date of first occurrence and date of resolution (if applicable)

CONFIDENTIAL Page 62 of 99

- Action taken
- Causal relationship
- Outcome of event (unknown, recovered, not yet recovered, recovered with sequelae, death [with date and cause reported]).

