#### 9.4.3.2 Adverse Events

Treatment-emergent adverse events (TEAEs), defined as those AEs occurring after the first administration of study treatment until the last study visit, will be tabulated in frequency tables by System Organ Class and Preferred Term based on the Medical Dictionary for Regulatory Activities (MedDRA) for each study phase. Additional summary tables will be provided for SAEs, AEs related to the study drug and/or study procedure, AESIs, and AEs leading to treatment discontinuation and study withdrawal. For a given AE, a subject will be counted once even if he/she has experienced multiple episodes of that particular AE.

Pre-treatment AEs will be listed separately.

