6.3. Missing Data

The primary method to impute the missing values for the efficacy assessments will be as follows:

Continuous Endpoints: To impute the missing values for efficacy continuous endpoints, Last Observation Carried Forward (LOCF) approach will be used. Only post-baseline visits will be imputed. Screening or Baseline information will not be used for LOCF. As sensitivity analysis, observed case (OC) will be conducted.

Binary Endpoints: All missing values will be treated as a Non-Responder for the binary endpoints. LOCF and OC will be used to impute the missing values as sensitivity analysis.

LOCF and Non-Responder will be performed to all subsequent, scheduled, missing post-baseline assessments. And when impute the missing data using LOCF and Non-Responder, all efficacy data after use the rescue therapy will be considered as missing. There will be no imputations for missing PK and Safety parameters. Imputation rules for missing dates in AEs and medications are described in the corresponding sections.

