7.6. Medication

Medications will be classified and presented on the ITT population as follows:

- Prior medications: defined as medications that started and ended prior to the first treatment date.
- Concomitant medications: defined as medications that started or ongoing or ended on or after the first treatment date.
- Rescue Medication: only medication that directly treat AD (mainly those that are approved or are standard of care), and include topical and systemic treatments. And Rescue medications will be classified by period (treatment period, follow-up period).
 - Rescue medication during treatment period is a medication which started from the first treatment date to the date of Week 16 (for week 16 completers) or the earliest date between 4 weeks after the last study drug injection or the date of early termination (for discontinued subject).
 - Rescue medication during follow-up period is a medication which started from the date of the post end of treatment period to the date of follow up visit.
- Background topical corticosteroids (TCS): permitted background TCS used throughout the study.

If the stop date and 'ongoing' are missing then the medication will be considered as concomitant medication. If stop date is partially missing, the medication will be considered as concomitant medication unless the non-missing part of date proves it ended prior to the first treatment date.

Medications (prior, concomitant and rescue medications) will be coded using Version Sept 2018 of the World Health Organization's Drug Dictionary (WHO DD). Preferred Anatomical Therapeutic Chemical (ATC) coding will be performed. Background TCS will not be coded.

The number and percentage of subjects with prior and concomitant medications will be summarized for the ITT population by the ATC Level 4 and the preferred drug name (PT), and sorted alphabetically by ATC level term and descending frequency of PT within ATC level term.

All rescue medications and topical rescue medications (route=topical) will be summarized by period (treatment and follow-up periods) for the ITT population by the ATC Level 4 and PT.

Prior, concomitant and rescue medication summaries will be sorted alphabetically by ATC level term and sorted in descending frequency of PT within ATC level term.

Background TCS will be summarized (number and percentage) by medication name for the ITT population and sorted in descending frequency of medication.

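### SAP 10.2 ignores the resolution date, so an adverse event recorded as over before the first injection becomes a TEAE if its onset date is missing, or is partial and does not prove a pre-dose start

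*SAP*

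**What the plan says.** SAP section 10.2 sets the definition: "Summaries of AEs will include only treatment emergent AEs (TEAEs) defined as AEs with an onset date/time on or after the date/time of first treatment". Two default rules follow for incomplete dates. For a wholly missing onset, "AEs with completely missing onset dates/time will be considered as TEAEs". For a partial onset, "the AE will be considered as TEAE unless the non-missing part of date/time proves it started prior to the first treatment date/time".

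No other part of the SAP adds to these rules. SAP section 6.3 only points back: "Imputation rules for missing dates in AEs and medications are described in the corresponding sections".

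Protocol section 9.4.3.2 gives the parent definition, in which TEAEs are "defined as those AEs occurring after the first" administration of study treatment, up to the last study visit. Pre-treatment events are to be listed separately, and SAP 10.2 includes such a listing. Protocol section 8.6.1 has events reported from the signing of the consent form, and its list of items to document for each event includes "Date of first occurrence and date of resolution (if applicable".

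**The concern.** Events are collected throughout a run-in of 2 to 4 weeks before Day 1, so the database will hold events that began and ended before any drug was given. For such an event the resolution date alone settles the classification: if it was over before the first injection, it started before the first injection. SAP 10.2 does not look at that date. When the onset is missing, or is too incomplete to decide, the event goes into the TEAE tables even though a recorded date shows that it meets neither the SAP's definition nor the protocol's.

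The incidence of adverse events, including TEAEs, is a primary safety endpoint. The TEAE tables are marked for the interim analysis, and most also go to the IDMC. Percentages are based on about 20 subjects, and about 10 at the interim, so a single event is visible in a row. SAP 10.2 also counts an event with missing relatedness as related, so a record lacking both items would enter the drug-related tables as well.

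**Working it through.** The documents give no figure to reproduce here. The check applies the SAP 10.2 rule literally to events that both started and ended before Day 1.

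**Inputs from the documents**
- Classification rules: SAP 10.2 (quoted above).
- Run-in: 2 to 4 weeks (SAP 3.3), taken as L = 14 or L = 28 days.
- Denominator: Safety population (SAP 10.2), about 20 subjects; about 10 at the interim (SAP 2.2).

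**Assumptions (not in the documents)**
- Onset is equally likely on each of the L days before Day 1.
- First-dose dates are spread evenly over the calendar (two years of dates in the calculation).

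**Step 1: an example.** Suppose the first injection is on 20 March 2020 and the event resolved on 12 March 2020. Every row below is in truth pre-treatment.

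| Recorded onset | Class under SAP 10.2 |
|---|---|
| Missing | TEAE (wrong) |
| 2020 | TEAE (wrong) |
| March 2020 | TEAE (wrong) |
| February 2020 | Not TEAE (right) |
| 8 March 2020 | Not TEAE (right) |

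**Step 2: how often the known part of the onset fails to decide.** With only month and year known, the rule misclassifies when the onset falls in the same calendar month as Day 1. If Day 1 falls on day d of a 30-day month, d − 1 earlier days lie in that month, so the share is the mean over d = 1 to 30 of min(L, d − 1)/L.
- L = 14: (0 + 1 + … + 14 + 15 × 14)/(30 × 14) = (105 + 210)/420 = 0.75.
- L = 28: (0 + 1 + … + 28 + 28)/(30 × 28) = (406 + 28)/840 = 0.52.

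Running the rule over two real calendar years gives the same picture:

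| Recorded onset | 14-day run-in | 28-day run-in |
|---|---|---|
| Missing | 100% | 100% |
| Year only | 98% | 96% |
| Month and year | 75% | 52% |
| Complete date | 0% | 0% |

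These shares are conditional on the record having that pattern. They are not expected error rates for the trial.

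**Step 3: effect on a table row.** Subjects are counted once per preferred term, so a misclassified event changes a row only if the subject has no on-treatment event of the same term. For k such subjects the row rises by k/N.
- N = 20: k = 1 gives 1/20 = 5 points; k = 2 gives 10 points.
- N = 10: k = 1 gives 1/10 = 10 points; k = 2 gives 20 points.

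The documents give no basis for choosing k, and k = 0 is quite possible.

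**Step 4: after the fix.** An event whose resolution date is known and precedes the first injection is classed as pre-treatment, so all the wrong rows in Step 1 become right. An event whose resolution date is also missing or undecidable stays a TEAE.

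**The case against.** Defaulting to treatment-emergent when the onset is unknown is a common and cautious convention. It can add an event to the tables but cannot hide one. The data pattern is also unusual: the event must start and resolve within a few weeks, have a usable resolution date, have an unusable onset date, and belong to a subject who is then dosed. Onset is an item to be documented for each event, events are asked about at both screening and baseline, and with about 20 subjects such a record should draw a query before lock. All TEAEs are listed by subject with missing date parts shown, so a careful reader could find it. All of this stands, and it is why the point is minor. It does not defend the rule itself: caution applies when timing is unknown, and here a recorded date settles it.

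Four stronger readings are tempting, and the documents do not support them.

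- **Every partial onset is misclassified.** It is not. SAP 10.2 already excludes an event when the known part of the onset proves an earlier start. On the assumptions above that removes 25% to 48% of month-and-year onsets.
- **The rule departs from the SAP's own convention for medications.** SAP 7.6 keeps a medication as concomitant "unless the non-missing part of date proves it ended prior to the first treatment date". It uses the stop date because its definition of a prior medication turns on when the medication ended. The TEAE definition turns on onset. Each rule tests the date in its own definition, and both default the same way.
- **The protocol prescribes a different missing-date rule.** Protocol 9.4.3.2 is silent on missing dates, and the protocol leaves further safety detail to the SAP. What holds is narrower: in this data pattern the SAP's default gives a result that neither definition allows.
- **The comparison with adults is biased.** The documents do not give the onset-date rule used in the adult studies. If it was the same, the error would run the same way on both sides. The interim comparison also has no stated formal safety test that one event could tip.

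**Conclusion.** The point holds, as a minor one. SAP 10.2 counts an event as a TEAE when its onset is missing, or is partial without proof of a pre-dose start, even if the recorded resolution date shows that it was over before the first injection. This is a stated rule that gives a wrong answer in a definable case, not merely a lack of detail, and no other section corrects it. It also takes the event out of the pre-treatment listing where it belongs.

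The direction is upward only. The size is 5 percentage points per affected subject in a preferred-term row at 20 subjects and 10 points at 10, provided that subject has no on-treatment event of the same term. How many subjects would be affected cannot be derived from the documents. It depends on how many onset dates stay incomplete after data cleaning, which is probably few. The 52% to 75% and 96% to 98% shares rest on the uniform-date assumptions; the 100% for a missing onset and the logical contradiction do not.

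**What to change.** Amend the incomplete-date rule in SAP 10.2 to this effect: an adverse event with a missing or partial onset is treatment-emergent by default, except where (a) what is known of the onset proves that it started before the date/time of first treatment, or (b) the resolution date/time, or what is known of it, proves that it ended before that point. Add that events excluded under (a) or (b) appear in the pre-treatment AE listing.

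The cost is one clause in the SAP and one extra condition in the derivation of the TEAE flag. It uses a date the protocol already requires, leaves truly undecidable events as TEAEs, and does not affect the conduct of the trial. It should be made before the relevant database lock.

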#### 8.6.2 Clinical Laboratory Evaluations

The hematology, clinical chemistry laboratory analyses, and urinalyses will be performed at a central laboratory. Reference ranges will be supplied and used by the investigator to assess the laboratory data for clinical significance and pathological changes.

The investigator or medically qualified co-investigator must review and evaluate laboratory values for each subject in a timely manner. For each out-of-range laboratory result, the investigator or designee will evaluate whether he/she considers it to be clinically significant, defined as meeting at least one of the following conditions:

- The abnormality suggests a disease and/or organ toxicity, or
- The abnormality is of a degree that requires additional active management, eg, discontinuation of the drug, close observation, more frequent follow-up assessments, or further diagnostic investigation.

If the investigator observes a clinically significant laboratory result, the test will be repeated as soon as possible and the subject will be monitored until the value returns to normal and/or an adequate explanation for the abnormality is found.

All clinically significant out-of-range laboratory values at the screening visit will be recorded (report a diagnosis rather than the laboratory value whenever possible). All clinically significant

CONFIDENTIAL Page 67 of 99

out-of-range laboratory values after the screening visit are to be reported as an AE if this abnormality was not present at the screening visit or is assessed as having worsened since the screening visit (ie, changed significantly from the screening visit). Whenever possible, the investigator should provide a diagnosis of an AE when reporting the abnormal laboratory value.

Subjects should be reminded to be well-hydrated before all visits for phlebotomy purposes. Subjects will be required to fast for at least 8 hours before the visits when blood chemistry testing is planned, except for the screening visit. The screening visit laboratory values must be available before the baseline visit.

Total blood volumes to be drawn at each visit are provided in the clinical laboratory manual. Additional samples may be required if medically indicated (eg, at unscheduled visits for safety reasons, when an abnormal laboratory value is observed and requires a re-test).

The following laboratory safety tests will be performed as specified in Section 7.2:

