#### 8.6.8 Physical Examination

Complete physical examination (PE) should be performed at all scheduled visits and any unscheduled visits for safety reasons, according to Section 7.2. A complete PE will include assessments of the head, ears, eyes, nose, throat, neck (including thyroid), skin/integumentary system, cardiovascular system, respiratory system (with respiratory assessment; see Section 8.6.9), gastrointestinal system, musculoskeletal system, lymph nodes, and nervous system.

Investigator should assess all abnormal findings for clinical significance. All clinically significant abnormal findings at the screening visit will be recorded in the Medical History form. Any clinically significant changes from the screening visit will be recorded as an AE.

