## 9.4.3.4 Clinical Laboratory

Laboratory data (absolute values and change from baseline) will be summarized. In addition, the number and percent of subjects below, within, and above the laboratory reference ranges will be summarized by visit. Shift tables will be generated using the reference ranges.

Abnormal laboratory values from tests performed on the baseline visit will not be considered as TEAEs, because the sample collection will be conducted before study drug administration.

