10.9. Other Safety

Confirmed pregnancy test results, childbearing potential, premense status results, biomarker and virology assessment data will be presented in a listing.

11. Immunogenicity

Blood samples will be collected to assess anti-drug (anti-nemolizumab) antibodies (ADA). Serum samples will be assessed for ADA at Baseline, Weeks 4, 8, 16, 24 and at any unscheduled visit for safety reasons.

Screening ADA, confirmation ADA, ADA titer, nutralizing antibodies, and treatment-related ADA will be will be summarized for the Safety population (scheduled visits only).

A treatment-related ADA is a post-baseline confirmatory ADA sample showing positive results while the baseline sreening or confirmatory ADA sample shows negative results.

All Immunogenicity data will be listed for the Safety population.

12. Health Economics

Not applicable.

13. Interim Analyses

An interim analysis is planned after approximately 10 subjects complete the Week 8 visit. The study will attempt to enrol at least 3 subjects with a low body weight (≤ 61 kg) for the interim analysis and approximately 6 total subjects with low body weight for the overall study population, with investigators attempting to enrol subjects at the lower age range (12-14 years old). The interim analysis will assess whether the observed safety and PK data from adolescents are similar to the data obtained in adults, which is the basis for allowing recruitment of adolescent subjects into the planned nemolizumab Phase 3 studies for AD (pivotal and open-label extension protocols).

Outputs presented for the interim analysis and for the IDMC are marked in Sections 18 (Index of Tables), Section 19 (Index of figures) and Section 20 (Index of Listings). But the selected output list for IDMC meeting can be updated by IDMC member's request.

14. Changes from Analysis Planned in Protocol

No changes to the methods planned in the protocol are foreseen.

15. Reference List

Not applicable.

16. Programming Considerations

All TLFs and statistical analyses will be generated using SAS® 9.4 or higher (SAS® Institute Inc., Cary, NC, USA). Computer-generated table, listings and figures (TLF) output will adhere to the following specifications.

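### SAP 10.2 has no exception for baseline-visit findings, so a pre-dose Day 1 laboratory event with no onset time can be counted as treatment-emergent, contrary to protocol 9.4.3.4

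*SAP*

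**What the plan says.** The protocol addresses the timing of TEAEs in two places. Section 9.4.3.2 gives the general rule: TEAEs are "defined as those AEs occurring after the first administration of study treatment until the last study visit". Section 9.4.3.4 adds a specific rule for laboratory data: "Abnormal laboratory values from tests performed on the baseline visit will not be considered as TEAEs", for the stated reason that the samples are taken before dosing.

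SAP 10.2 uses a different boundary. TEAEs are "defined as AEs with an onset date/time on or after the date/time of first treatment". For incomplete onset information it says: "If AE onset date/time is partially missing, the AE will be considered as TEAE unless the non-missing part of date/time proves it started" before first treatment. SAP 10.3, on laboratory evaluations, says nothing about how a baseline-visit abnormality reported as an AE is to be classified. SAP 14 states: "No changes to the methods planned in the protocol are foreseen".

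Three other protocol provisions matter:

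- Section 8.6.2 makes baseline laboratory AEs possible. Clinically significant "out-of-range laboratory values after the screening visit are to be reported as an AE if this abnormality was not present at the screening visit" or has worsened since then.
- The notes to the schedule in section 7.2 require the laboratory sample at an injection visit to be drawn no more than 30 minutes before the injection.
- The AE data list in section 8.6.1 asks for "Date of first occurrence and date of resolution (if applicable" and does not mention a clock time.

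**The concern.** The protocol settles the status of baseline-visit laboratory abnormalities by design: the sample precedes the drug, so the finding cannot be treatment-emergent. The SAP replaces that with a comparison of recorded dates and times, and resolves doubt in favour of TEAE. Where only a date is available, the design information is lost and the SAP rule returns the answer that the protocol rules out.

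TEAE incidence is a primary safety endpoint (protocol 6.2.3), and SAP section 18 marks the main TEAE tables for both the interim analysis and the IDMC. The interim asks whether adolescent safety resembles adult safety, as the basis for admitting adolescents to Phase 3. With one arm and few subjects, there is no concurrent control in which the same misclassification would also appear.

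**Working it through.** The plan states no figure on this point to reproduce, so the check is a comparison of texts followed by simple arithmetic for scale.

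**Tracing one event through the rules**

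1. A subject's baseline sample shows a clinically significant value that was absent at screening. Protocol 8.6.2 requires an AE.
2. The sample was drawn on Day 1, within 30 minutes before the first injection (protocol 7.2 notes). The assessment order in protocol section 8 also puts blood collection before dosing. An AE dated to that sample carries the Day 1 date.
3. If only the date is recorded, the onset date equals the date of first treatment. It satisfies the SAP's on-or-after test at date level, and under the partial-date rule it cannot prove earlier onset. Both routes give TEAE.
4. Protocol 9.4.3.4 gives not a TEAE.

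| Day 1 event | Onset time recorded before injection | No onset time recorded |
|---|---|---|
| From baseline laboratory test | SAP: not TEAE. Protocol 9.4.3.4: not TEAE. Agree. | SAP: TEAE. Protocol 9.4.3.4: not TEAE. **Conflict.** |
| From another pre-injection assessment | SAP: not TEAE. Protocol 9.4.3.2: not TEAE. Agree. | SAP: TEAE. Protocol 9.4.3.2: not TEAE if onset preceded dosing. **Conflict.** |
| Timing truly unknown | Not applicable | SAP: TEAE. The protocol gives no specific rule; the default is reasonable. |

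The second row arises because other findings can also become AEs. For the physical examination, protocol 8.6.8 says: "Any clinically significant changes from the screening visit will be recorded as an AE". Investigator assessments come before dosing in the visit order.

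**Size per subject**

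Inputs: N = 20 planned (protocol 9.5) and about 10 at the interim (SAP 13). Each subject counts once, over the Safety population (SAP 10.2). For a subject with no other TEAE, the change in overall incidence is 1/N:

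- Final: 1/20 = 5.0 percentage points.
- Interim: 1/10 = 10.0 percentage points. This takes the interim denominator as 10; if more subjects have been dosed by the cut-off, the step is smaller.

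**Chance that it arises at all**

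The documents give no rate. Let p be the share of subjects with a reportable pre-dose Day 1 AE. This is an assumption, shown as a range. P(at least one) = 1 − (1 − p)^N, and the expected number is Np.

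| Assumed p | N=10: P(≥1) | N=10: expected | N=20: P(≥1) | N=20: expected |
|---|---|---|---|---|
| 1% | 9.6% | 0.1 | 18.2% | 0.2 |
| 5% | 40.1% | 0.5 | 64.2% | 1.0 |
| 10% | 65.1% | 1.0 | 87.8% | 2.0 |

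These are upper limits on the chance of a changed overall incidence, because the event must also lack an onset time and the subject must have no other TEAE.

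**The case against.** The strongest reply has four parts.

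*The SAP expects a time.* SAP 10.2 is written in terms of date and time throughout. If the CRF collects AE onset time and a pre-dose time is entered, the SAP definition already excludes the event. This stands: the problem is conditional, and the protocol's date-only list is the sole evidence that time may be absent.

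*The protocol rule still applies.* The SAP is meant to detail the protocol's analyses, and SAP 14 foresees no change, so 9.4.3.4 could be read as remaining in force. This does not hold. SAP 10.2 is not silent on the case; its default assigns the event to TEAE. A programmer who follows it literally departs from the protocol without any declared change.

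*Onset is not detection.* The protocol asks for the date of first occurrence and prefers a diagnosis to a laboratory value or sign. A condition that began in the run-in and was only noticed on Day 1 would carry an earlier date and be classed correctly. This stands, and it narrows the problem, chiefly for examination findings.

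*The consequence is small.* The AE analyses are descriptive, no decision threshold is stated, and the default over-counts, which is the cautious direction for safety. This stands as to size. It does not justify a classification that the protocol expressly excludes.

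**Conclusion.** The point holds in conditional form. When no onset time is recorded, SAP 10.2 can class a pre-dose Day 1 laboratory AE as treatment-emergent, against protocol 9.4.3.4, with no declared change. The effect on overall TEAE incidence is 5 points at N=20 or 10 points at N=10 for each affected subject who has no other TEAE. Frequency is unknown, and the direction is over-counting. The conclusion assumes that the AE is dated to the Day 1 sample and that onset time is missing. The fault is the missing exception, not the default.

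A reader might infer four stronger things that the documents do not support:

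- That 9.4.3.4 also excludes examination or vital-sign findings. It names laboratory values only; the others fall under the general definition in 9.4.3.2.
- That pre-dose Day 1 findings will certainly enter the tables. They must be clinically significant, new or worse since screening, dated Day 1 and without a time, and the CRF is not available to settle the last condition.
- That every misclassified event moves overall incidence. A subject with another TEAE is already counted.
- That these events would reach the drug-related tables because SAP 10.2 treats missing relatedness as related. That also needs a blank causality entry, which the protocol requires for every AE.

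**What to change.** Add to SAP 10.2:

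- AEs based on laboratory tests performed at the baseline visit are pre-treatment AEs (protocol 9.4.3.4), whether or not an onset time is recorded.
- Day 1 AEs documented as arising from any other assessment made before the first injection are pre-treatment AEs (protocol 9.4.3.2), whether or not an onset time is recorded.
- All other Day 1 AEs of unknown timing keep the TEAE default.

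Derive the classification from recorded assessment and injection times where these exist. Protocol 8.2.1 already has PK sample times and the injection time at the same visit entered in the CRF. For baseline laboratory tests no time is needed, since the design fixes the order. If the CRF can still be changed, a before/after first injection flag for Day 1 AEs would settle the remaining cases.

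The cost is a short SAP addition and a small derivation. SAP listing 16.2.7.2 already exists to hold pre-treatment AEs, so no event is lost from view. The cautious treatment of events whose timing is truly unknown is unchanged.
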